#### 8.1.3. Iron Chelation Therapy

Concurrent treatment with iron chelation therapy should be used as per product label and investigator practice prior to randomization.

#### 8.1.4. RBC Transfusions

Concurrent treatment for anemia with blood transfusions is allowed, at the discretion of the Investigator, for low hemoglobin levels, symptoms associated with anemia (eg, hemodynamic or pulmonary compromise requiring treatment) or comorbidity.

For any RBC transfusions received during the study, collect hemoglobin values just prior to transfusion, the number of units transfused, the dates of transfusion. If available, the volume transfused in mL at each transfusion and hematocrit (Hct) of the transfused unit should be collected.

Each TD subject will have a “pre-transfusion hemoglobin threshold” for requiring transfusion during the study which will be determined based on transfusion history. Baseline pre-transfusion hemoglobin threshold will be the mean of all documented pre-transfusion hemoglobin values during the 24 weeks prior to Dose 1 Day 1. During treatment, if the pre-transfusion hemoglobin level is increased by  $\geq 1$  g/dL compared to the pre-transfusion hemoglobin threshold for that subject, transfusion should be delayed by a minimum of 7 days and/or the number of units transfused should be reduced by 1 or more RBC units.

Subjects may be transfused at the Investigator’s discretion for symptoms related to anemia or other requirements (eg, infection).

## 8.2. Prohibited Concomitant Medications and Procedures

No concurrent treatments with any other investigational agent are allowed.

Treatment with hydroxyurea and anagrelide is not allowed during the Treatment Period (refer also to Section 8.1.2).

The use of hematopoietic growth factors will not be allowed during the Treatment Period of the study. However, any subject who requires hematopoietic growth factor treatment during the Treatment Period must be discontinued from the study, at which point, hematopoietic growth factor treatment is permitted.

Anticoagulant therapies and platelet aggregation inhibitors can be used. However, if these therapies are used due to a related AE that would qualify for Treatment Discontinuation as per Section 11, the subject should be discontinued from the study treatment. Any anticoagulant therapies use for prophylaxis, as well as aspirin and LMW heparin are allowed.

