The dose of luspatercept or placebo for each subject can be delayed and/or reduced as per the dose modification, dose reduction and dose delay guidelines as detailed in Table 5. Subjects will be discontinued from study treatment as appropriate, for reasons listed in Section 11.

The decision to discontinue a subject from study treatment remains the responsibility of the treating physician; the Sponsor will not delay or refuse it. However, prior to a decision of discontinuing a subject, it is recommended that the Investigator contact the medical monitor and forward appropriate supporting documents for review and discussion.

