### 3.1.3. Long-term Treatment Period

At the investigator's discretion, subjects completing the 48-week double-blind Treatment Period will be able to continue receiving the IP to which they were initially randomized (ie, luspatercept or placebo) in a double-blind Long-term Treatment Period for up to 48 weeks after the first dose of the last subject or until the date of unblinding.

The double-blind Long-term Treatment Period will continue until all subjects have either completed 48 weeks of the double-blind Treatment Period or discontinued before reaching 48 weeks of the double-blind Treatment Period, or in the event the study is unblinded per Data Monitoring Committee (DMC) recommendation. Treatment during the Long-term Treatment

Period is subject to dose titration, dose delay and dose reduction, and treatment discontinuation as described in Section 7, Table 4 and Table 5.

Subject's dose titration should be reviewed with the Sponsor and performed in the IVRS.

Dose titration during the Long-term Treatment Period is allowed. Dose titration rules are defined as described in Table 4 and Section 7.2.1.1. Please refer to Section 8.1.3 for concomitant iron chelation therapy use and Section 8.1.4 for concomitant RBC transfusions.

Subjects will be discontinued from study as appropriate, for reasons listed in Section 11.

Subjects who continue to receive treatment with luspatercept or placebo when the study is unblinded (approximately 48 weeks after the first dose of the last subject) may opt to continue receiving luspatercept in the Open-label Phase or to discontinue treatment and enter the Post-treatment Follow-up Period.

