### 3.1.5. Post-treatment Follow-up Period

All subjects who discontinue treatment will undergo a 156-week Post-treatment Follow-up Period, following the last dose of IP.

All subjects who discontinue treatment after completion of at least 48 weeks of the double-blind Treatment Period will enter the Post-treatment Follow-up Period for 156 weeks (ie 3 years). Subjects who enter the Long-term Treatment Period or Open-label Phase and discontinue treatment during those periods, will also enter the Post-treatment Follow-up Period for 156 weeks. The Post-treatment Follow-up Period will begin after the last IP dose is received, as per the visit schedule laid down in protocol Table 3 (ie, 9-week follow-up, Week 24, and every 24 weeks after the last dose up to Week 144, follow-up by End of Study visit at Week 156).

Early discontinued subjects, ie, subjects who discontinue before completing 48 weeks in the double-blind Treatment Period, will continue to be monitored on Week 9, followed by Week 24, Week 48, Week 72, Week 96, Week 120, Week 144 after the last dose up to Week 156 (assessments defined in Table 3, Table of Events).

When the study is unblinded: (i) subjects on luspatercept stay in the Post-treatment Follow-up Period for up to 156 weeks; (ii) subjects on placebo will stay up to unblinding and will be moved to the Open-label Phase after fulfilling appropriate eligibility criteria (refer to Section 3.1.4).

[figure not shown]
Refer to the subject management decision tree detailed in Figure 5.

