-  LTTP will end when all subjects completed 48 weeks of double-blind treatment or discontinued before reaching 48 weeks double-blind treatment, whichever is the earlier date, or at the time the study is unblinded (per DMC recommendation). Only subjects that do not discontinue for reasons as described in Section 11 can enter in the LTTP.
-  Only for subject who discontinue prior to completion of 48 weeks in the double-blind Treatment Period.
-  End of Study visit can occur at any time up to at least 156 weeks post last dose.
-  HCV-RNA test and HBsAg and/or HBVDNA .
-  +/- 10 day window around for MRI assessments and DXA is allowed (MRI for LIC, myocardial iron, spleen and LVEF). These assessments to be performed as indicated on specified week, regardless of dose delays. MRIs and DXA scans performed within the 4 weeks prior to the ICF signature can be accepted, if subject does not show any relevant clinical symptoms judged by the Investigator as sufficient reason to repeat these procedures within the Screening/Run-in period and agreed with the Sponsor.
-  Placebo subject who discontinued the study, but were compliant with the protocol 48 weeks post Dose 1 Day 1, and continued their participation in the Post-treatment Follow-up Period until the time of unblinding, refer to Section 3.1.4.
-  For all subjects on treatment at the time of Open-label Phase initiation, continue with the appropriate dose number.
-  For subjects who have documented diagnosis of  $\beta$ -thalassemia in their medical history, by other methodology or do not have a source laboratory report in the medical files, the  $\beta$ -thalassemia genotype can be done at any time during the course of the study.
-  The same Cardiac Doppler Echocardiography technique should be used within a subject throughout the study duration.
-  As per standard of care.
-  Follow-up visits at Weeks 9, 24, 48, 72, 96, 120, 144 and 156 post last dose should be performed by all subjects, regardless if a subject has Early Discontinued or not.
-  For early discontinuation subjects, these parameters to be reported up to 48 weeks Post Dose 1 Day 1 or Week 9 post last dose whichever is the later date.

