## 11. DISCONTINUATIONS

### 11.1. Treatment Discontinuation

Subjects will have a treatment discontinuation visit at the time of study drug discontinuation. All subjects who received at least one dose of the study drug will be followed for 156 weeks post-treatment.

The following events are considered sufficient reasons for discontinuing a subject from the investigational product(s):

- Adverse Event(s):
  - Any serious AE assessed as related to luspatercept
  - Any AE  $\geq$  Grade 3 assessed to be related to luspatercept if the event causes a treatment delay of 15 weeks or longer from the prior administered dose, including hypersensitivity to luspatercept.
  - If a subject experiences  $> 2$  Dose Reductions due to related AE
- Any new malignancy
- Withdrawal of consent - An indication that a study participant has removed itself from the study treatment
- Death
- Lost to follow-up - the loss or lack of continuation of a subject to follow-up
- Pregnancy
- If dose is delayed for more than 15 weeks or longer from the prior dose administered dose due to AE, including case of elective surgery/hospitalization
- Other: Different than the one(s) previously specified or mentioned

The reason for discontinuation of treatment should be recorded in the eCRF and in the source documents.

The decision to discontinue a subject from treatment remains the responsibility of the treating physician, which will not be delayed or refused by the Sponsor. However, prior to discontinuing a subject, the Investigator may contact the Medical Monitor and forward appropriate supporting documents for review and discussion.

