### 11.2. End of Study

The following events are considered sufficient reasons for discontinuing a subject from the study:

- Screen failure
- Completed study per protocol
- Withdrawal of consent - An indication that a study participant has removed itself from the study

- Death
- Lost to follow-up - The loss or lack of continuation of a subject to follow-up
- Other: Different than the one(s) previously specified or mentioned

The following events **may be** considered sufficient reasons for discontinuing a subject from the study:

- Adverse events(s) - Any untoward medical occurrence in a subject or clinical investigation subject administered a pharmaceutical product and which does not necessarily have a causal relationship with this treatment. An adverse event (AE) can therefore be any unintended sign (including an abnormal laboratory finding), symptom, or disease temporally associated with the use of a medicinal (investigational) product, whether or not related to the medicinal (investigational) product. NOTE: For further information, see the ICH Guideline for Clinical Safety Data Management: Definitions and Standards for Expedited Reporting. [Modified from ICH E2A] Synonyms: side effect, adverse experience. See also serious adverse event, serious adverse experience

The reason for End of Study should be recorded in the eCRF and in the source documents.

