**1.6. Concomitant Medications**

**1.6.1. Removed references for medication leading to treatment discontinuation from sections other than Section 8.2**

Rationale:

Medications that will trigger treatment discontinuation are described in the prohibited medications section (Section 8.2). For clarity, and consistency references to such medications have been removed from other sections.

Revised Sections: Section 8 and Section 8.1.1.

**1.6.2. Anticoagulant therapies used during the study treatment are allowed as long as the medications are not used due to a related adverse event (AE) that would qualify for treatment discontinuation**

Rationale:

Clarified that the use of anticoagulant therapies will trigger treatment discontinuation only if such therapies are used due to a related AE that would qualify for treatment discontinuation as per Section 11 of the protocol.

Revised Section: Section 8.2.

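### Section 8.2 discontinues a subject who needs a haematopoietic growth factor from the study, where study treatment is very probably meant; read literally, it conflicts with the 156-week follow-up

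*Protocol*

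**What the plan says.** Protocol Section 8.2 bars haematopoietic growth factors during the Treatment Period and adds that "any subject who requires hematopoietic growth factor treatment during the Treatment Period must be discontinued from the study", after which the growth factor may be given.

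Three other places require follow-up once study drug stops:

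- Section 11.1: "All subjects who received at least one dose of the study drug will be followed for 156 weeks post-treatment".
- Section 3.1.5: "All subjects who discontinue treatment will undergo a 156-week Post-treatment Follow-up Period, following the last dose of IP".
- Table 3 footnote 23: the visits from Week 9 to Week 156 after the last dose "should be performed by all subjects, regardless if a subject has Early Discontinued or not".

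None of the three makes an exception for growth-factor use. Section 11.2, whose list opens "The following events are considered sufficient reasons for discontinuing a subject from the study", does not name it. Nor does the list of reasons for stopping treatment in 11.1. In either list only the residual category, Other, could cover it, so 8.2 is the only specific instruction for this event.

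**The concern.** Leaving the study and stopping study drug have different consequences in this protocol. A subject who only stops drug moves into scheduled follow-up. A subject who leaves the study does not, and the note at the end of Section 3.1.4 says that someone who leaves before unblinding without completing follow-up cannot return for open-label luspatercept.

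The rule is mandatory. A site that applied it literally would remove a subject who may be willing to stay. That subject would lose the scheduled visits that support safety follow-up, including the malignancy check due at least every 24 weeks (Table 3 footnote 26). Data collection to 48 weeks after Dose 1 for early discontinuers (footnote 24, Section 6.6.1) would stop as well.

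**Working it through.** **1. Which meaning is intended?** The sentence in 8.2 points to study exit, but the surrounding text points to stopping drug:

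- Table 3 footnote 18 describes placebo subjects as having discontinued the study while they remained in post-treatment follow-up until unblinding. Section 3.1.4 describes the same group as having discontinued treatment.
- Section 3.1.2 has "Subjects will be discontinued from study treatment as appropriate, for reasons listed in Section 11". Section 3.1.3 has the same sentence as "Subjects will be discontinued from study as appropriate, for reasons listed in Section 11", and 3.1.4 repeats that version.
- Sections 8 and 8.1.1 use the same shorthand when they discuss medications that may require discontinuation.
- Section 8.1.2 stops study drug for hydroxyurea and sends the subject to follow-up. The anticoagulant rule in 8.2 itself stops study treatment. These rules cover other drugs, so they do not contradict the growth-factor rule; they show the usual pattern.
- The amendment rationale (item 1.6.1), used here only as evidence of purpose, describes 8.2 as the place for medications that trigger treatment discontinuation.

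**2. Visits at stake under the literal reading.** Footnote 23 lists Weeks 9, 24, 48, 72, 96, 120, 144 and 156 after the last dose, which is 8 visits. Week 156 is the End of Study visit, which may be held at any time (footnote 15, Section 6.7) and so could take place at exit. The loss is therefore at most 8 − 1 = 7 visits. For placebo subjects it is smaller, because Section 3.1.5 keeps them in follow-up only until unblinding, before possible open-label entry. Section 3.1.3 puts unblinding about 48 weeks after the last subject's first dose. If that last subject were on placebo, at most about 3 visits (Weeks 9, 24 and 48) would come first.

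**3. Transfusion endpoints.** SAP Section 10 sets the cutoff for the primary report as

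cutoff = min(death, study discontinuation, last dose + 20 days, 11MAY2018).

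A subject whose cutoff precedes the end of a response interval is a non-responder. SAP Section 5.1 ends the two intervals on Day 169 and Day 337. Records more than 20 days after the last dose are unused under either reading, so the readings can differ by at most 20 days of data.

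- Dose 8 on schedule: 1 + 7 × 21 = Day 148; cutoff 148 + 20 = Day 168, before Day 169. Non-responder under both readings.
- Dose 16 on schedule: 1 + 15 × 21 = Day 316; cutoff 316 + 20 = Day 336, before Day 337. Non-responder under both readings.
- Dose 9 (Day 169) or Dose 17 (Day 337) on schedule: the interval has already been reached.

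The readings can differ only if the last dose falls on Days 149–168 or 317–336, exit is recorded before Day 169 or Day 337, and the subject otherwise meets the response definition. One such subject moves a response rate by 1/200 = 0.5 points (luspatercept) or 1/100 = 1.0 point (placebo), against a planned difference of 40% − 20% = 20 points.

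**4. Sample size.** The planned 300 reproduces with a continuity-corrected two-proportion formula: 90 placebo and 180 luspatercept, and 270/0.9 = 300. With z = 1.96 and a pooled rate of 1/3, SE₀ = √(0.2222 × (1/90 + 1/180)) = 0.0609 and SE₁ = √(0.16/90 + 0.24/180) = 0.0558. Power is Φ((0.20 − 0.0083 − 1.96 × 0.0609)/0.0558) = 90.3%, or 92.6% without the correction term 0.0083. No input depends on 8.2.

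**The case against.** The best case against raising this is that the protocol already settles it. Three categorical statements require follow-up, 11.2 does not name growth factors as a reason to leave, and footnote 18 shows that discontinuing the study can mean stopping drug and staying in follow-up. A misreading may also be caught, because Section 6 sends protocol questions to the medical monitor and Section 3.1.2 recommends contact before a subject is discontinued. Most of this stands, and it makes the conflict one of wording. It does not remove the conflict: 8.2 is mandatory and specific, and the Other entry in 11.2 gives a literal reader a route to study exit.

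A reader might infer three stronger things that the documents do not support.

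- *That the sponsor chose to end follow-up for these subjects.* Nothing states such an intention, and the usage set out above points the other way.
- *That the primary result is biased or under-powered.* Section 9.6.1 says off-treatment transfusion records will be used, so their loss looks important, but the SAP cutoff already excludes them beyond 20 days. Suppose instead that 1%, 2% or 5% of would-be responders (assumed; the documents give no rate) became non-responders in both arms. Uncorrected power at 180/90 would go from 92.6% to 92.2%, 91.8% or 90.6%. If the loss were in the luspatercept arm only, it would be 91.6%, 90.6% or 86.8%. Neither the rate nor the one-sided loss has any basis in the text.
- *That the lost follow-up would hide malignancies selectively.* Table 5 does link cytopenias to a work-up for haematologic malignancy, but it never mentions growth factors, and the recording duty in Section 10.1 survives.

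**Conclusion.** The concern holds as a wording conflict of low priority. For an affected luspatercept subject the literal reading costs at most 7 of 8 scheduled visits; for a placebo subject it costs fewer. Possible loss of open-label access matters mainly for placebo subjects, since Section 3.1.4 already makes luspatercept subjects who stopped double-blind treatment ineligible by default, apart from an exception on the investigator's request.

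How many subjects this touches is unknown and probably very small: recent use of erythropoiesis-stimulating agents is an exclusion (Section 4.3, number 12), Section 1.1.2.3.6 says these agents are seldom used in this disease, and the rule covers only the 48-week Treatment Period. No meaningful change to any efficacy result, to the sample size or to power follows. The conclusion assumes that a site would take 8.2 at its word. The view that this is a slip is an inference from usage and cannot be proved.

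**What to change.** In the growth-factor sentence of Section 8.2, replace the words *the study* with *study treatment and enter the Post-treatment Follow-up Period*, and keep the closing clause that then permits the growth factor. This matches the hydroxyurea rule in 8.1.2. The follow-up schedule already exists, so the cost is one phrase. Naming growth-factor use in the 11.1 list is optional and not needed.

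The SAP (Section 15.1) reports that the 48-week period was complete at the primary analysis, so a short check of study-exit records would show whether anyone was removed under this sentence. The exit categories in SAP Section 6 would not reveal it, because they do not name growth-factor use.

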## 8.3. Required Concomitant Medications and Procedures

Not applicable.

## 9. STATISTICAL CONSIDERATIONS

### 9.1. Overview

The proposed Phase 3 study is double-blind, randomized, placebo- controlled, multicenter study to determine the efficacy and safety of luspatercept (ACE-536) plus BSC versus BSC in adults who require regular red blood cell transfusion due to  $\beta$ -thalassemia.

The design of the study, including the proposed targeted patient population, study endpoints, and statistical plan, is discussed below.

### 9.2. Study Population Definitions

Study populations to be analyzed are defined as follow:

**Intent-to-treat (ITT):** The ITT population will consist of all randomized subjects regardless of whether or not the subject received IP. All efficacy analyses will be conducted for the ITT population and will be analyzed based on randomization group.

**Safety:** The safety population will consist of all subjects who were randomized and received at least one dose of IP. Subjects will be included in the treatment group corresponding to the IP they actually received.

Statistical methods to handle missing data will be described in the SAP. The SAP will describe any predefined rules for including/excluding any subjects with data from any analyses (eg, time windows, visit by visit analysis, endpoint analysis, protocol violation).

### 9.3. Sample Size and Power Considerations

Based on data in the luspatercept Phase 2 (A536-04/A536-06) study the assumed targeted response rate for the primary endpoint is 40% in luspatercept group and 20% for the placebo group. A total sample size of 300 (200 in the luspatercept group, 100 in placebo group) will have 90% power to detect the difference between the luspatercept group and the placebo group with a 2-sided alpha of 0.05 and assumed 10% drop-out rate for each treatment group.

#### Randomization and Stratification

Subjects will be randomized to receive luspatercept or placebo at a 2:1 ratio. Randomization will be accomplished by an IRT to ensure timely registration and randomization. A stratified randomization schedule will be implemented. Randomization will be stratified by: Geographical regionsa:

- North America and Europe
- Middle East and North Africa
- Asia-Pacific

a See [Appendix E](#) for list of countries within each region.

### 9.4. Background and Demographic Characteristics

Subjects' age, height, weight, and baseline characteristics will be summarized using descriptive statistics, while gender, race and other categorical variables will be provided using frequency

tabulations by dose cohort. Prior transfusion history will be summarized. Medical history data will be summarized using frequency tabulations by the Medical Dictionary for Regulatory Activities (MedDRA) system organ class and preferred term. Beta-thalassemia diagnoses as well as RBC transfusion dependence will be summarized using frequency tabulations.

